11. DEMOGRAPHIC AND OTHER BASELINE CHARACTERISTICS

Demographic data and other baseline characteristics will be presented for the ITT Set and SAF Set.

No formal statistical testing will be carried out for comparing demographic or other baseline characteristics between treatment groups.

The following demographic and other baseline characteristics will be reported for this study:

Demographics

- Age (years) calculated as (Date of Informed Consent – Date of Birth)/365.25;
- Gender;

- Race;
- Ethnic

Other Baseline Characteristics

- Waist circumference (cm), if collected in inches then $\text{Waist circumference (cm)} = \text{Waist Circumference (in)} * 2.54$;
- Weight (kg), if collected in lbs then $\text{Weight (kg)} = \text{Weight (lbs)} * 0.4536$;
- Height (cm), if collected in inches then $\text{Height (cm)} = \text{Height (in)} * 2.54$;
- Body Mass Index (BMI) (kg/m^2), where $\text{BMI} (\text{kg}/\text{m}^2) = \text{weight} (\text{kg}) / \text{height} (\text{m})^2$

Page 10

— 1 —

— 1 —

1000

10 of 10

Digitized by [contact]

Digitized by [contact]

Digitized by [contact]

11. **What is the primary purpose of the study?**

Digitized by [contact]

© 2013 Pearson Education, Inc. All Rights Reserved. May not be copied, scanned, or duplicated, in whole or in part. Due to electronic rights, some third party content may be suppressed from the eBook and/or eChapter(s). Editorial review has determined that any suppressed content does not materially affect the overall learning experience. Pearson Education, Inc. reserves the right to remove additional content at any time if subsequent rights restrictions require it.

- Baseline efficacy parameters, including rater-administered MADRS total score, CGI-BP-S

INTRA-CELLULAR THERAPIES INC. (ITCI)

STATISTICAL ANALYSIS PLAN: PROTOCOL ITI-007-402

Page 25 of 63

INTRA-CELLULAR THERAPIES INC. (ITCI)

STATISTICAL ANALYSIS PLAN: PROTOCOL ITI-007-402

Page 26 of 63

15. EFFICACY OUTCOMES

15.1. PRIMARY EFFICACY

15.1.1. PRIMARY EFFICACY ENDPOINT AND DERIVATION

The primary efficacy variable is change from baseline in rater-administered MADRS total score to Week 6 (Day 43). The MADRS is a 10-item checklist designed to measure the overall severity of depressive symptoms. The MADRS individual items are rated by a qualified site rater at each site on a scale of 0 to 6 in which a score of 6 represents the most severe symptoms for each item assessed. The MADRS total score is the sum of all 10 items and ranges from 0 to 60. If one or more items are missing at a visit, the total score will also be set to missing for that visit.

In addition to the rater-administered MADRS assessment, a self-administered MADRS assessment will be conducted. At screening, the self-administered MADRS assessment will be conducted prior to the rater-administered one. At all other visits, the rater-administered MADRS assessment will be conducted first. Self-administered MADRS scores will be compared to the ones from the rater-administered MADRS assessment on an ongoing basis as part of a remote quality assurance program.

15.1.2. MISSING DATA METHODS FOR PRIMARY EFFICACY ENDPOINT

The primary analysis method for evaluating the primary efficacy endpoint is the likelihood-based analysis of repeated measures, MMRM, described in details in Section 15.1.3. The use of MMRM inherently implies that the treatment effect on the change from baseline in the rater-administered MADRS total score will be similar for the patients who withdraw and for those who complete the study in their respective treatment groups, conditional on the outcomes observed prior to withdrawal (MAR assumption). To assess the robustness of the MAR assumption, sensitivity analyses which utilize multiple imputations and a different assumption about unobserved outcomes will be performed, as detailed in Section 15.1.4.

15.1.3. PRIMARY ANALYSIS OF PRIMARY EFFICACY ENDPOINT

The treatment effect on the primary efficacy endpoint will be evaluated using an MMRM model for the ITT Set. The model will include the change from baseline at each pre-specified timepoint as the response variable and study visit, the adjunctive treatment and bipolar disorder stratification variables, baseline MADRS total score, site (or pooled site), baseline MADRS total score-by-study visit interaction, treatment (ITI-007 40 mg, ITI-007 60 mg, placebo), and

treatment-by-study visit interaction. An unstructured covariance matrix will be used to model the correlation among repeated measurements within patient. In the event the convergence cannot be attained with the unstructured correlation matrix, the following alternative structures will be attempted in the specified order: heterogeneous Toeplitz structure (TOEPH), heterogeneous autoregressive(1) (ARH(1)), heterogeneous compound symmetry (CSH), No Diagonal Factor Analytic (FA0(q), with q equal to the number of time points), Toeplitz structure (TOEP), autoregressive(1) (AR(1)), and compound symmetry (CS). The Kenward-Rogers method will be used to estimate the denominator degrees of freedom. The treatment and treatment-by-time interaction terms allow for comparisons of the treatment groups at each of the following time points: Weeks 1, 2, 3, 4, 5, and 6 (Days 8, 15, 22, 29, 36, and 43). Treatment differences will be evaluated via contrasts for the time-by-treatment factor. This methodology will be used to compare the treatment groups versus placebo for change from baseline at each time point.

Estimates of model parameters will be presented, as well as least-squares mean (LSM) estimates for change from baseline in MADRS score, standard errors and 95% confidence intervals (CI) for LSMs will be presented by treatment group and time point. Contrast estimates (LSMs) for between-group comparisons (ITI-007 60 mg vs. placebo and ITI-007 40 mg vs. placebo), the corresponding standard errors, 95% CIs, effect sizes, and p-values will be presented for each visit. Effect size will be calculated for each ITI-007 dose group (vs. placebo) as $\frac{\text{LS Mean Difference}}{\text{Pooled estimate of within patient error standard deviation}}$. For the primary and key secondary efficacy endpoints, the effect size will be obtained.

The empirical cumulative distribution function of the percent change from baseline in MADRS total score at Day 43 will be provided. The horizontal axis corresponds to increasing levels of improvement, with a vertical line anchoring an improvement of 50%. The vertical axis corresponds to the percent of patients achieving each level of response. Patients discontinuing the study are considered non-responders and represented by the left-most portion of the graph. This responder analysis corresponds to the utility estimand (Permutt, 2016) as it incorporates both patients discontinuation status as well as the improvements in MADRS total score.

[REDACTED]

[REDACTED]

[REDACTED]

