6.8 Pregnancy

Pregnancy is not regarded as an AE unless there is a suspicion that an investigational product may have interfered with the effectiveness of a contraceptive medication. Any pregnancy that occurs during study participation must be reported using a clinical study pregnancy form. To ensure patient safety, each pregnancy must be reported to the Sponsor within 2 weeks of learning of its occurrence. The pregnancy must be followed up to determine outcome (including spontaneous miscarriage, elective termination, normal birth, or congenital abnormality) and status of mother and child, even if the patient was discontinued from the study. Pregnancy complications and elective terminations for medical reasons should not be reported as an AE or SAE. Spontaneous miscarriages must be reported as an SAE.

Completion of the pregnancy form is not required for screen-failed patients who have had positive pregnancy test(s).

Any SAE occurring in association with a pregnancy brought to the Investigator's attention after the patient has completed the study, and considered by the Investigator as possibly related to the study treatment, must be promptly reported to the Sponsor.

7 Statistical and Analytical Plan

A formal and detailed statistical analysis plan (SAP) will be finalized prior to the planned interim analysis and will provide further details regarding the definition of analysis endpoints, analysis methodology, and the interim analysis to address all study objectives. Changes made to the data analysis methods as described in this protocol will be documented in the SAP and will not necessitate a protocol amendment. All departures from the statistical analyses described in the approved protocol, whether made before or after unblinding, will be documented, and justified in the final clinical study report.

A blinded data review will be conducted prior to unblinding the patients' treatment assignments for assessing the accuracy and completeness of the study database and defining analysis sets.

[figure not shown]

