7.5.4 Analysis of Primary Efficacy Endpoint

The study is designed to evaluate the efficacy profile of ITI-007 40 mg and 60 mg based on the change from baseline to Day 43 in the MADRS total score.

The treatment effect on the primary efficacy endpoint will be evaluated using a mixed-effect model repeated measures (MMRM) method. The model will include the change from baseline at each pre-specified time point in the rater-administered MADRS total score as the response variable, and visit, treatment group, site (or pooled site), and the stratification variables, first-line treatment (lithium or valproate) and Bipolar Disorder type at screening (I or II), and interaction term for treatment group-by-visit interaction as fixed effects, and the baseline MADRS total score and baseline MADRS total score-by-visit interaction as covariates. The patient term will be included in the model as a random effect and other terms as fixed effects. The treatment group-by-site (or pooled site) interaction term will not be included in the MMRM model for the primary efficacy analysis. Rather, it will be examined as part of the exploratory analysis. An unstructured covariance matrix will be used to model the correlation among repeated measurements within patient. In the event the convergence cannot be attained with the unstructured correlation matrix, the following alternative structures will be attempted in the specified order: heterogeneous Toeplitz structure (TOEPH), heterogeneous autoregressive (1) (ARH[1]), heterogeneous compound symmetry,

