No Diagonal Factor Analytic (FA0(q), with q equal to the number of time points), Toeplitz structure (TOEP), autoregressive (1) (AR[1]), and compound symmetry. Model parameters will be estimated using restricted maximum likelihood. The Kenward-Roger approximation will be used to estimate the denominator degrees of freedom. The treatment group and treatment group-by-visit interaction terms allow for comparisons of the treatment groups at each of the following: Days 8, 15, 22, 29, 36, and 43. Treatment differences will be evaluated via contrasts for the treatment group-by-visit factor. This methodology will be used to compare each of the ITI-007 doses, 40 mg and 60 mg, to placebo for change from baseline at each day. Estimates of model parameters will be presented, as well as LSM estimates for change from baseline in MADRS total score, standard errors and 95% CIs for LSMs will be presented by treatment group and day. Contrast estimates (LSMs) for between-group comparisons, the corresponding standard errors, 95% CIs, effect sizes, and p-values will be presented for day.

A number of sensitivity analyses of the primary efficacy endpoint will be performed to explore the robustness of the MMRM results under a different assumption on the mechanism of missing data. All sensitivity analyses will be performed based on the Sensitivity Set. The MMRM method assumes a missing-at-random mechanism for missing data. That is, the probability that measurements are missing depends on the set of observed measurements but is unrelated to the specific unobserved missing values that, in principle, should have been obtained. Sensitivity analyses will be conducted to assess the impact of missing data under different assumptions on the mechanism of missing data and will be detailed in the SAP.

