4. STUDY DESIGN

4.1. GENERAL DESCRIPTION

Study participation will last approximately 10-12 weeks (up to 9 visits) and will include the following periods: a *Screening Period*, lasting up to 2 weeks (unless medical monitor approves longer); an *On-Treatment Period* of 6 weeks of daily administration of study medication, and a *Safety Follow-up Period* of approximately 2 weeks after last dose of study medication (or within 1 week of early termination, if possible). The timing and assessments during each study period are described in the Schedule of Events (Table 6-1 of the protocol and Appendix 1 of this SAP).

Approximately 520 patients (173 patients/ treatment group) will be randomized in a 1:1:1 ratio to receive one of three study treatments: 40-mg ITI-007, 60-mg ITI-007, or placebo at approximately 93 global sites. The sample size estimation assumes a common dropout rate of 15% at Day 43, and a common within-patient correlation of 0.7 for the change from baseline in MADRS total scores at Days 8, 15, 22, 29, 36 and 43. This will provide approximately 90% power to detect an effect size of 0.4.

The primary analysis strategy will be based on overall ITT patients and will follow the study protocol.

An alternative analysis strategy specific for Non-US submissions will be considered, details on this approach can be found in Appendix 4 of this SAP.

4.2. [REDACTED]

[REDACTED]

[REDACTED]

[REDACTED]

Sections 7.5.4 and 7.5.6 of the protocol discuss adding the treatment-by-site (or pooled site)

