All investigative sites with fewer than 2 ITT patients per treatment group will be pooled as follows: The largest site with fewer than 2 ITT patients per treatment group will be pooled with the smallest site with fewer than 2 ITT patients per treatment group within the same country or geographic region. If this results in a pooled site still having fewer than 2 ITT patients per treatment group, this site will be pooled together with the next smallest investigative site within the same country or geographic region, if one exists; otherwise, no further pooling is needed. Sites with the same number of ITT patients will be ordered in ascending order of their numerical site identification number. This will serve as a tie-breaker rule in case multiple sites have the same number of ITT patients. Should the primary efficacy analysis model present convergence issues, after testing the sequence of correlation structures, then the site effect will be reconsidered and may be dropped from the model. These pooled investigative sites, as determined based on the primary efficacy response variable, will be used for any analysis that has investigative site as a fixed effect in the model. The actual investigative site numbers will be included in the listings. For sensitivity analyses where site is a factor, additional pooling will be performed starting from the ITT pooled sites. Sites with patients who are in SEN Set but not ITT will be pooled, using the same algorithm as outlined above.

The default significance level for statistical tests will be 5%; confidence intervals will be 95% and all tests will be two-sided, unless otherwise specified in the description of the analyses. All analyses will be conducted using SAS® version 9.4 or higher.

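### Optional: if the unstructured fit fails, FA0(q), which is the unstructured covariance in another form, should be the first fallback for the primary model and not the fourth

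*SAP*

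**What the plan says.** SAP 15.1.3 states: "An unstructured covariance matrix will be used to model the correlation among repeated measurements within patient". The repeated measures are at Days 8, 15, 22, 29, 36 and 43, so there are six time points. If the fit does not converge, the fallbacks are taken in a fixed order: TOEPH first, then "heterogeneous autoregressive(1) (ARH(1)), heterogeneous compound symmetry (CSH), No Diagonal Factor Analytic (FA0(q), with q equal to the number of time points", then TOEP, AR(1) and CS.

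Protocol 7.5.4 has the same order: "heterogeneous Toeplitz structure (TOEPH), heterogeneous autoregressive (1) (ARH[1]), heterogeneous compound symmetry", followed by "No Diagonal Factor Analytic (FA0(q), with q equal to the number of time points), Toeplitz structure (TOEP" and the three homogeneous structures. The two documents do not contradict each other.

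On inference, SAP 15.1.3 says: "The Kenward-Rogers method will be used to estimate the denominator degrees of freedom". The visible text names no robust (sandwich) variance for use with a constrained structure.

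SAP section 7 gives the step after the list is exhausted: "after testing the sequence of correlation structures, then the site effect will be reconsidered and may be dropped from the model". SAP section 4.2 also cites the alternative structures as a reason for not using the protocol's second round of site pooling. The covariance list is therefore the SAP's main remedy for non-convergence.

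**The concern.** FA0(q) with q equal to the number of time points is not a simplification of unstructured. It is the same covariance family in a form that cannot leave the non-negative definite region. An iteration on the raw variances and covariances can step outside that region and fail; one on the triangular factor cannot.

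The list therefore gives up the planned covariance before trying its more stable form. If TOEPH converges, it carries the Day 43 test and FA0(6) is never fitted. With model-based inference, a constrained structure that does not hold misstates the Day 43 standard error in either direction. That affects the error rate or power of 60 mg against placebo on MADRS. This is step 1 of the fixed sequence in SAP 7.2, and every later test depends on it.

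**Working it through.** **Inputs from the documents.** Six visits; 173 patients per arm; 15% dropout by Day 43; effect size 0.4; two-sided 5% tests; and "a common within-patient correlation of 0.7 for the change from baseline in MADRS total scores" (SAP 4.1, Protocol 7.2).

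**The plan's own figure.** Power = Φ(0.4·√(n/2) − 1.96), with n the effective number per arm.
- n = 173 × 0.85 = 147.05: Φ(3.43 − 1.96) = 92.9% for one dose.
- n = 173/1.0713 = 161.5 (MMRM variance inflation at correlation 0.7, dropout rising linearly from 0 to 15%): Φ(3.594 − 1.96) = 94.9%. With dropout of 2.5% per visit the inflation is 1.0867 and power is 94.6%.
- Both doses through the fixed sequence (test statistics correlated 0.5): 91.0% and 90.6% for the two MMRM cases.

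The stated figure of about 90% is reproduced as power for both doses and is conservative for one. The point below does not depend on it.

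**Parameter counts, t = 6.**
- Unstructured: t(t+1)/2 = 6·7/2 = 21
- FA0(q), q = 6: q(2t−q+1)/2 = 6·7/2 = 21
- TOEPH: 2t−1 = 11
- ARH(1) and CSH: t+1 = 7 each
- TOEP: 6; AR(1) and CS: 2 each

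The fallback list therefore runs 11, 7, 7, 21, 6, 2, 2.

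**Equivalence on data.** In one simulated data set (520 patients, 86% observed at the last visit), the maximised −log-likelihood was 6027.8496 for both unstructured and FA0(6). The largest difference in any covariance element was 5e-5. TOEPH gave 6088.8, ARH(1) 6093.1 and CSH 6457.8.

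**Effect of a constrained structure.** Assumptions: 3% dropout at each of Days 15, 22, 29, 36 and 43 (5 × 3% = 15%), unrelated to outcome; arm-by-visit means only, with no site or baseline terms; large samples. Each structure V is fitted to a true covariance S by minimising Σₖ pₖ[log|Vₖ| + tr(Vₖ⁻¹Sₖ)] over dropout patterns k. The model SE comes from the inverse information and the true SE from the sandwich formula. The true level is 2Φ(−1.96 × model SE/true SE). For example, TOEPH under S4 gives 2Φ(−1.96 × 0.911) = 7.4%.

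S1 is the documents' planning correlation. S2 to S5 are assumed, with mean correlation about 0.70:
- S1: 0.7 throughout.
- S2: correlation by lag .81, .72, .64, .56, .48; SDs 5.5, 6.5, 7.4, 8.2, 8.9, 9.6.
- S3: independent random intercept (SD 4.0) and slope (SD 1.2 per visit), residual SD 3.2.
- S4: adjacent correlations .76, .82, .86, .89, .91, others their products; SDs as S2.
- S5: S4's adjacent correlations in reverse order; SDs as S2.

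| Covariance | SE ratio TOEPH / ARH(1) / CSH | True level |
|---|---|---|
| S1 | 1.000 / 1.013 / 1.000 | 5.0 / 4.7 / 5.0% |
| S2 | 1.000 / 1.006 / 1.017 | 5.0 / 4.9 / 4.6% |
| S3 | 0.926 / 0.926 / 0.974 | 7.0 / 7.0 / 5.6% |
| S4 | 0.911 / 0.912 / 0.990 | 7.4 / 7.4 / 5.2% |
| S5 | 1.126 / 1.121 / 1.062 | 2.7 / 2.8 / 3.7% |

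Under S5, power at effect size 0.4 is 3.6, 3.5 and 2.4 points below FA0(6).

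A further assumed covariance (adjacent correlations rising from 0.65 to 0.87, SDs 5 to 10, about 14% dropout) gave 7.9 / 7.8 / 5.4%, against 5.0% for unstructured or FA0(6). As a finite-sample check, 4,338 simulated null trials under S3 fitted by REML gave 7.1% for TOEPH and 5.1% for FA0(6), with Monte Carlo SE at most 0.4 points. That simulation was not repeated when the table was recomputed.

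**Do these covariances cause failure?** In 1,000 simulated null trials under each of S1, S3 and S4, the unstructured maximum existed in all 3,000. FA0(6), started from a diagonal matrix, reached it in 180 of 180 trials checked.

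**The case against.** **The benefit is unproven where it counts.** FA0(6) is used only when unstructured has failed, and none of the calculations is restricted to such trials. If the failure reflects a singular optimum, FA0(6) may stop on the same boundary. This stands. It limits the claim to trying the planned model's other form first; it does not show that FA0(6) will rescue the fit.

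**No inflation under the planning assumption.** At a common correlation of 0.7, TOEPH and CSH are correctly specified and ARH(1) is slightly conservative. The other covariances are assumed, and the direction for this trial is unknown. This stands.

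**The overall effect is very small.** If unstructured failed in 1 to 10% of trials, a hypothetical rate, and the worst S4 level applied, overall alpha would be 0.99 × 5 + 0.01 × 7.4 = 5.02% to 0.90 × 5 + 0.10 × 7.4 = 5.24%. With no failures in 1,000 S4 trials, the 95% upper bound on the failure rate is about 0.3%, giving 0.997 × 5 + 0.003 × 7.4 = 5.007%. The simulation omitted site and baseline terms and software behaviour, so actual failure could be more frequent. This stands and sets the grade.

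**A parsimony-first order is defensible.** Stepping down after a 21-parameter fit fails is reasonable in itself. This order is not that rule, because it goes from 11 to 7 to 7 and then back up to 21. This part does not stand.

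**Another cause of failure is possible.** Protocol 7.5.4 also includes patient as a random effect, which is not identifiable beside an unstructured or FA0(6) within-patient covariance. If it were fitted, reordering would not help. SAP 15.1.3 does not list the term.

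**Conclusion.** The point holds as an optional, free improvement. The order of the list and the equivalence of FA0(6) with unstructured are certain. The list is pre-specified and the same in both documents, so this is a contingency rule that can be improved, not an error.

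Its size depends on two unknowns: whether unstructured fails, and the true covariance. Given failure, the level of the Day 43 test could be unaffected (common correlation 0.7), raised to 7.0–7.4% under TOEPH or ARH(1) in S3 and S4, or lowered to 2.7–3.7% with some loss of power in S5. These are large-sample figures, with dropout unrelated to outcome, and are not conditioned on failure. With about 520 patients and six visits, failure should be uncommon and the expected effect on overall alpha is slight.

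**What to change.** In SAP 15.1.3, make FA0(q), with q equal to the number of time points, the first fallback after unstructured. Keep TOEPH, ARH(1), CSH, TOEP, AR(1) and CS in their present order. If FA0(6) also fails or reaches a singular boundary, the sequence continues as it does now, and the site-effect step in SAP section 7 is unchanged. If the key secondary model (SAP 15.2) uses the same list, apply the same order there.

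Make the change before unblinding and record it in the SAP. The opening of Protocol section 7 says that changes to the analysis methods "will be documented in the SAP and will not necessitate a protocol amendment". The SAP cites protocol version 1.6 of 23 March 2020, while the protocol supplied is dated 04 September 2019. The list in version 1.6 should be checked before the edit is described as a departure from Protocol 7.5.4.

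The cost is one item moved in one list. It needs no patients, data or alpha, and has no effect if unstructured converges.

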7.2 Sample Size Calculations

The sample size calculation of the study is based on the primary efficacy endpoint, the change from baseline to Day 43 in MADRS total score. Adjusting for multiple comparisons of two ITI-007 treatment groups with placebo by using the fixed sequence procedure (test the 60 mg vs placebo first, and if statistically significant then proceed to test the 40 mg placebo vs placebo), a sample size of approximately 520 patients (173 per group) will provide approximately 90% power to detect an effect size of 0.4. This sample size estimation also assumes a common dropout rate of 15% at Day 43, and a common within-patient correlation of 0.7 for the change from baseline in MADRS total scores at Days 8, 15, 22, 29, 36, and 43.

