7.2. MULTIPLE COMPARISONS/ MULTIPLICITY

The study is designed to evaluate the primary and key secondary efficacy endpoints of two doses of ITI-007, 60 mg and 40 mg versus placebo, which involves multiple comparisons. A fixed sequence procedure will be used to control the overall Type I error rate.

The primary and key secondary efficacy endpoints will be tested in the following order:

- 1) ITI-007 60 mg vs placebo comparison change from baseline in MADRS total score at Day 43;
- 2) ITI-007 60 mg vs placebo comparison change from baseline in CGI-BP-S Depression score at Day 43;
- 3) ITI-007 40 mg vs placebo comparison change from baseline in MADRS total score at Day 43;
- 4) ITI-007 40 mg vs placebo comparison change from baseline in CGI-BP-S Depression score at Day 43

All tests will be performed at the 0.05 level. If at any step a hypothesis test does not show statistical significance, then all hypotheses at subsequent steps will not be tested for significance and their p-values will be reported for descriptive purposes only.

There will be no multiplicity adjustments for the comparison of other secondary or exploratory endpoints.

[REDACTED]

[REDACTED]

[REDACTED]

[REDACTED]

[REDACTED]

[REDACTED]

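### The last three covariance fallbacks (TOEP, AR(1), CS) assume one variance for all visits and have no robust standard error: a low-severity gap in a remote contingency of the primary MMRM

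*SAP*

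**What the plan says.** SAP 15.1.3 models change in MADRS total score at Days 8 to 43 with an unstructured covariance. If that fit does not converge, these structures are tried in order: TOEPH, ARH(1), CSH, FA0(q) with q equal to the number of time points, and then the last three. The text ends the list and moves straight to inference: "Toeplitz structure (TOEP), autoregressive(1) (AR(1)), and compound symmetry (CS). The Kenward-Rogers method will be used to estimate the denominator degrees of freedom". Protocol 7.5.4 has the same list and adds the estimation method: "Toeplitz structure (TOEP), autoregressive (1) (AR[1]), and compound symmetry. Model parameters will be estimated using restricted maximum likelihood". Neither section names an empirical (sandwich) standard error for any fallback.

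SAP section 7 says what follows if convergence problems remain: "after testing the sequence of correlation structures, then the site effect will be reconsidered and may be dropped from the model". The whole list is therefore used before the site term is touched. SAP section 4.2 also drops the protocol's second round of site pooling as a remedy for non-convergence.

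On the error rate, SAP 7.2 states "All tests will be performed at the 0.05 level" and SAP section 7 states "confidence intervals will be 95% and all tests will be two-sided". The Day 43 MADRS comparison of 60 mg with placebo is the first test in the fixed sequence. The 40 mg comparison comes from the same model.

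**The concern.** TOEP, AR(1) and CS each estimate a single variance for all six visits. If the spread of change scores widens over time, the Day 43 contrast gets a standard error reflecting an average over visits, which is smaller than the one Day 43 warrants. Kenward-Roger is a small-sample adjustment computed from the fitted covariance model, so it carries the error through. The confidence interval would be too narrow and the test would exceed its stated level, at the first step of the sequence and again for 40 mg. Choosing a different standard error after seeing the convergence failure would be a post hoc decision on unblinded data, so the rule needs to be written beforehand.

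**Working it through.** **Inputs from the documents.** Two-sided 0.05 (SAP 7 and 7.2); "Approximately 520 patients (173 patients/ treatment group) will be randomized in a 1:1:1 ratio" (SAP 4.1); "This sample size estimation also assumes a common dropout rate of 15% at Day 43" (Protocol 7.2); common within-patient correlation 0.7 over the six visits (Protocol 7.2, SAP 4.1).

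**Input not given.** No SD of change is visible for any visit. I write r for SD(Day 43)/SD(Day 8) and show a range.

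**The plan's own figure first.** Protocol 7.2 says the sample "will provide approximately 90% power to detect an effect size of 0.4". Completers per arm: 173 × 0.85 = 147. SE of the standardised difference: √(2/147) = 0.1166. Power: Φ(0.4/0.1166 − 1.96) = Φ(1.47) = 92.9%. With the information an MMRM recovers at correlation 0.7 (effective n about 161.5 per arm), power is 94.9%. Power to win both MADRS tests is 87.8% on completers and 91.0% with MMRM. The stated figure of approximately 90% is therefore reproduced to within about 2 points as power for both doses, and is conservative for 60 mg alone. It does not depend on the visit SDs.

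**Hand check, complete data, CS.** With arm-by-visit means and no missing data, the Day 43 estimate is the difference of Day 43 means, while CS uses the average of the six variances. So SE(model)/SE(true) = RMS(SD)/SD(Day 43), and actual size = 2Φ(−1.96 × that ratio).

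- For r = 2 with a linear rise, the SDs relative to Day 43 are 0.5, 0.6, 0.7, 0.8, 0.9 and 1.0.
- Mean square = (0.25 + 0.36 + 0.49 + 0.64 + 0.81 + 1)/6 = 3.55/6 = 0.592, with root 0.769.
- Size = 2Φ(−1.96 × 0.769) = 2Φ(−1.507) = 13.2%.

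**With dropout.** For each structure I found the limiting likelihood fit under monotone dropout to 15% and true correlation 0.7. I then compared the model-based variance of the Day 43 contrast with its true variance. Actual size of the nominal 5% test:

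| r | TOEP / AR(1) / CS, linear rise | Range, most of the rise early |
|---|---|---|
| 0.8 (SD falls) | 2.6 / 2.4 / 2.6% | 2.8-3.2% |
| 1.0 | 5.0 / 4.7 / 5.0% | same |
| 1.2 | 7.4 / 7.0 / 7.4% | 6.4-6.6% |
| 1.5 | 10.3 / 9.9 / 10.4% | 8.2-8.4% |
| 2.0 | 13.8 / 13.2 / 14.1% | 10.3-10.4% |

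For CS with a linear rise, the SE ratios behind the r = 1.2, 1.5 and 2.0 rows are 0.913, 0.829 and 0.751. If the true correlation is instead autoregressive at 0.85, the linear-rise figures are 7.3-7.9%, 10.2-11.0% and 13.4-14.6%; at constant SD, CS then gives about 5.6%.

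**Simulation check.** REML fits, 173 per arm, 3,000 runs per cell, CS / AR(1): r = 1.0 gives 5.3 / 4.1%; 1.2 gives 7.0 / 6.9%; 1.5 gives 10.2 / 9.0%; 1.9 gives 13.3 / 12.6%, each to within about 1 point.

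**Isolating the cause.** At r = 1, 1.5 and 2, CSH gives 5.0% and ARH(1) gives 4.7%. The constant-variance restriction is what does the damage. In a separate simulation (1,500 trials per setting, Day 8 SD at 50%, 65% or 80% of Day 43), sandwich standard errors on the CS and AR(1) fits gave 4.3-5.8%.

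**The case against.** **The trigger is remote.** Five structures must fail before TOEP is tried, and each of them allows the Day 43 variance to differ from the rest. FA0(6) is a Cholesky form of the full unstructured matrix, so the plan already makes a second full-covariance attempt. About 441 completers (3 × 147) support 21 covariance parameters (6 × 7/2). The documents give no basis for a probability of reaching TOEP, so the unconditional effect on type I error cannot be stated; it is probably very small. This stands, and it sets the severity.

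**The variance pattern is assumed.** A reader might infer that reaching one of these fallbacks is enough to inflate the test. The documents do not support that. The sample size rests on a standardised effect and one common correlation, and nothing says the SD rises. With constant SD the size is about 5%, and with a falling SD the test is conservative.

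**Other analyses offer a cross-check.** The LOCF ANCOVA in Protocol 7.5.4 needs no visit covariance. SAP 15.1.2 points to multiple-imputation analyses in 15.1.4, which is redacted. Neither would replace the primary p-value, so the gap in the primary rule remains.

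**The calculations are simpler than the planned model.** They omit site, baseline and strata terms, and dropout does not depend on outcome. The SAP assumes data missing at random, under which a wrong covariance can also bias the point estimate. I have not quantified that. It favours removing the structures over changing their standard error.

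**Conclusion.** The gap is real, conditional and of low severity. If the unstructured, TOEPH, ARH(1), CSH and FA0(6) fits all fail, and if the SD of MADRS change rises over visits, the rule as written gives a Day 43 test above its stated 5%. With a linear rise, the size is about 7%, 10% and 13-14% at SD ratios of 1.2, 1.5 and 2.0. If most of the rise comes early, it is about 6.5%, 8.3% and 10.4%. These figures assume 173 per arm, 15% monotone dropout unrelated to outcome and, except where stated, correlation 0.7.

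Two stronger readings go too far. The planned primary test is not inflated, because the unstructured fit estimates the Day 43 variance directly. Nor is Kenward-Roger a problem across the whole fallback list: TOEPH, ARH(1) and CSH also estimate that variance separately and do not have this flaw.

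**What to change.** Preferred: delete TOEP, AR(1) and CS from the list in SAP 15.1.3. After FA0(6), the next step is then the site-effect step already in SAP section 7. The cost is three fewer fallbacks.

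Alternative: keep them and add a sentence such as: If TOEP, AR(1) or CS is used, standard errors, confidence intervals and p-values will come from the empirical (sandwich) covariance estimator with between-within degrees of freedom; Kenward-Roger applies to the unstructured, TOEPH, ARH(1), CSH and FA0(6) fits. The cost is one sentence, one software option and a slightly more variable standard error. The sandwich was checked here on CS and AR(1) but not on TOEP.

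Deletion is cleaner because a sandwich standard error does not correct any bias in the estimate from a wrong covariance under outcome-dependent dropout. Protocol section 7 allows analysis changes to be documented in the SAP without a protocol amendment, so either option can be made there.
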